## 4.3 Protocol Exceptions and Deviations

Exceptions to the above eligibility criteria will not be granted. It is expected that subjects will meet all eligibility criteria. Departures from the protocol should be avoided unless required for the safety of the subject. Protocol deviations will be documented by the study monitor and will be included in the final clinical study report. Protocol deviations should be submitted to the Institutional Review Board (IRB) in accordance with the site's IRB requirements.

## 4.4 Subject Withdrawal Criteria

Subjects may voluntarily withdraw from the study or be removed from the study at the discretion of the Investigator or designee, or Sponsor at any time. The Investigator or designee may withdraw a subject at any time if it is determined that continuing in the study would result in a significant safety risk to the subject.

If such withdrawal occurs or if the subject fails to return for EoS, the Investigator or designee should determine the primary reason for a subject's premature withdrawal from the study and record the reason in the subject's study records.

Premature withdrawal may occur for any of the following reasons:

- Non-compliance with the protocol requirements
- Pregnancy
- Death
- AE
- Subject request
- Investigator or designee request
- Sponsor request

If a subject withdraws or is withdrawn after randomization and administration of study drug under the above criteria or for any other reason, study staff should make every effort to complete the full panel of assessments scheduled until 4 hours after study drug administration. The reason for subject withdrawal must be documented.

If a subject withdraws or is withdrawn from the study due to an adverse event (clinical or laboratory), the subject will be instructed to return to the clinic for, at a minimum, the evaluations scheduled for EoS. If the adverse event has still not resolved, additional follow-up will be performed as appropriate and documented. As a minimum requirement, AEs should be followed for at least 1 week after the subject's dose of study medication.

For subjects who are lost to follow-up (i.e., those subjects whose status is unclear because they fail to appear for study visits without stating an intention to withdraw), the Investigator or designee should show "due diligence" by documenting in the source documents all steps taken to contact the subject, e.g., dates of telephone calls, registered letters, etc.

Any subject who discontinues from the study between Screening and dosing in Dosing Period 1 may be replaced.

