#### 5.4.2 Other Restrictions

Subjects will be confined to the Phase 1 unit for each dosing period from **Day -1 to Day 2.** Subjects will be discharged after the last assessment has been performed within that period (at least 30 hours post-dose for PK sample). In case of persisting adverse events, the subject may remain in the unit at the discretion of the Investigator or designee.

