## 7.6 Vital Signs

Vital signs, measured after at least 5 minutes supine, will include supine systolic blood pressure (SBP), supine diastolic blood pressure (DBP), heart rate (HR), respiration rate (RR), and oral body temperature. All vital sign measurements will be performed by appropriately qualified and authorized study personnel, using appropriate equipment.

BP and HR will be measured if possible in the same arm at each visit by using automated devices. BP results will be recorded in millimeters of mercury (mmHg). HR will be measured in the humeral artery in the dominant arm for approximately 30 seconds and will be recorded as beats per minute (bpm). RR will be measured and recorded in breaths per minute. Oral body temperature will be measured in degrees Celsius.

At Screening and for interim and study exit vital signs, subjects who have a supine systolic BP > 135 mm Hg or < 90 mm Hg or who have a supine diastolic BP > 85 mm Hg or < 50 mm Hg will undergo at least one BP reassessment within 15 minutes of the original. Subjects who have a heart rate > 90 bpm or < 50 bpm will undergo at least one heart rate reassessment within 15 minutes of the original. All out of range results will be assessed by the PI, Sub-Investigator, or designee.

If interim BP or heart rate values are deemed clinically significant, subjects should be monitored by study staff and if deemed necessary from a safety standpoint, the patient will be discontinued.

Vital signs will be taken at Screening and at EoS. During each dosing period, they will be taken at check-in on Day -1, on Day 1 within 60 minutes of dosing and 1, 2, 4, and 8 hours after dosing, and on Day 2, 24 hours after dosing. Assessments will be performed at the nominal times +/- 15 minutes.

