### 7.9.5 Unipolar Take drug again VAS

Subjects will rate "I would take this drug again' on the unipolar scale using the anchors:

- 0: Definitely not
- 100: Definitely so

The unipolar take drug again VAS will be completed on Day 1 within 60 minutes prior to dosing and on Day 2 at 24 hours +/- 20 minutes after dosing.

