# 7.14.2 Treatment Emergent Adverse Events (TEAE)

A TEAE will be an AE that occurred during the study after a subject ingested the dose of study drug until 48 hours post-dose or that was present prior to dosing and exacerbated after the dose of study drug. This pertains to all dosing periods.

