#### 6.4.9.1 PK Parameter Estimation

Pharmacokinetic parameters  $C_{max}$ ,  $T_{max}$ ,  $AUC_{0\text{-tlast}}$ ,  $AUC_{0\text{-inf}}$ ,  $t_{1/2}$ ,  $\lambda_z$ , CL/F, Vz/F will be estimated. The exact time of sample collection, relative to time of dose, will be used in the analyses. No imputation of missing samples will occur. If a scheduled sample's concentration is missing, the pharmacokinetic analyses will be conducted as if that sample had not been scheduled for collection. The time of dosing will be considered as time 0 and the pre-dose assessment will be treated as if it occurred at time 0. Any subject with sufficient data to adequately characterize their concentration-time profile will be included in the pharmacokinetic analyses. If the terminal half-life for any case is physiologically implausible, and a suitable set of terminal concentrations cannot be selected from the semi logarithmic concentration-time plot, then no elimination parameter estimates will be reported.  $t_{1/2}$  can only be estimated for those cases where the apparent elimination rate constant has been estimated.

Descriptive statistics will be presented for each PK parameter for each study medication by treatment period (Lasmiditan and, Sumatriptan). All PK parameters will be listed.

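### After a dosed subject withdraws, Protocol 4.4 asks for assessments only to 4 hours post-dose, so that period's later readings, scheduled to 30 hours, are not required and are at risk

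*Protocol*

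**What the plan says.** Protocol 4.4 covers withdrawal for any reason once a subject has been randomized and dosed. In that case "study staff should make every effort to complete the full panel of assessments scheduled until 4 hours after study drug administration".

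The schedule for the same dose runs much longer:

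- Protocol 7.6 sets post-dose vital signs at "1, 2, 4, and 8 hours after dosing, and on Day 2, 24 hours after dosing". Section 7.8 also takes ECGs to 24 hours.
- The DEQ-5 (7.9.7) runs to 24 hours, and the drug-liking, high and sedation VAS (7.9.1 to 7.9.3) run to 8 hours.
- The overall-liking and take-again VAS (7.9.4, 7.9.5) are read pre-dose and then only "on Day 2 at 24 hours +/- 20 minutes after dosing".
- PK sampling (7.13) runs to 30 hours.

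Confinement matches this schedule. Protocol 5.4.2 states: "Subjects will be discharged after the last assessment has been performed within that period (at least 30 hours post-dose for PK sample".

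Two further provisions bear on the point. Protocol 7.6 and 7.7 allow a subject to be discontinued when interim blood pressure, heart rate or orthostatic results are judged clinically significant and safety requires it. SAP 6.4.7 summarises vital signs at each time point only for subjects who have both a baseline value and a value at that time.

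**The concern.** In a single-dose crossover, withdrawal during a period cannot shorten the exposure for that period. It only removes dosing in later periods. Section 4.4 does not separate stopping further dosing from stopping assessment of the dose already taken, and it sets the collection target well short of the planned observation window.

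Vital signs and ECGs are part of the protocol's primary endpoint. A marked early vital-sign response is itself a route to discontinuation. A subject who leaves by that route then need not supply the 8-hour and 24-hour values, and the SAP's vital-sign summary uses only the values present. The SAP gives no other missing-data rule for ECG, VAS or DEQ-5. The late summaries may therefore come disproportionately from subjects with a milder response, in a study meant to compare the combination with each drug alone.

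**Working it through.** **1. Readings beyond the 4-hour target.** Counted from the protocol's detailed schedule (Table 2) and sections 7.6 to 7.13. The counts are the most at risk for one subject-period. A subject who leaves at, say, 12 hours has already given the 8-hour readings.

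| Measure | Post-dose times | After 4 h | Share |
|---|---|---|---|
| Vital signs | 5 | 2 (8, 24 h) | 40% |
| Orthostatic vital signs | 2 | 0 | 0% |
| ECG | 7 | 2 (8, 24 h) | 29% |
| DEQ-5 | 5 | 2 (8, 24 h) | 40% |
| Drug-liking, high, sedation VAS (each) | 4 | 1 (8 h) | 25% |
| Overall-liking, take-again VAS (each) | 1 | 1 (24 h) | 100% |
| PK samples | 14 | 6 (6, 8, 12, 16, 24, 30 h) | 43% |

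End-of-study or early-termination readings (Protocol 3.3.5) do not replace values at 8 and 24 hours after the dose.

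**2. Possible bias in a late mean.** Suppose N subjects receive a treatment and k have no late value. The observed mean minus the full mean equals (k/N) × (mean of those observed − mean of those missing). The protocol enrols 42 so that 36 finish, an allowance of 6/42 = 14.3%. The documents do not say how many of the six would withdraw during a period.

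- k = 1: 1/42 = 2.4% of the gap between the two means.
- k = 6, all in the same treatment (the extreme of the allowance): 6/42 = 14.3% of that gap.

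The size of the gap is unknown.

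**3. PK power, starting from the plan's own figure.** Protocol 8.5 claims at least 80% power with 36 subjects, a within-subject CV of 25% and limits of 80 to 125%. The true ratio is not stated, so it is taken here over a range.

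- σ = √ln(1 + 0.25²) = 0.246. SE = 0.246 × √(2/36) = 0.058, with 35 degrees of freedom.
- Exact power of two one-sided 5% tests with 36 pairs: 0.966 at ratio 1.00, 0.895 at 0.95, 0.815 at 0.93, 0.763 at 0.92. The claim is reproduced for true ratios of about 0.93 or nearer 1.
- With all 42 pairs: 0.985 at ratio 1.00 and 0.933 at 0.95.

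The most that better collection could add is the step from 36 to 42 pairs: 0.966 to 0.985, or 0.895 to 0.933.

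**4. Comparability of an AUC that stops at 4 hours.** The documents give no half-life or absorption rate, so this step is an assumption. In a one-compartment oral model, C(t) ∝ e^(−kt) − e^(−ka·t), with half-life 2 to 8 h and ka 0.7 to 2.0 per hour, the integral over 0 to 4 h is 22% to 70% of the integral over 0 to 30 h. Such an AUC is not comparable with a full one. Cmax would mostly have been sampled.

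**The case against.** The case on the other side is substantial, and several parts of it stand.

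- **The data are not lost.** A reader might infer that everything after 4 hours disappears. Section 4.4 sets a minimum effort and forbids nothing later. A willing subject may still be assessed, and 5.4.2 lets a subject with a persisting adverse event remain in the unit. The readings are at risk because nobody is asked to obtain them.
- **Adverse events are largely protected.** They are one of the three primary measures. After withdrawal for an adverse event, "the subject will be instructed to return to the clinic for, at a minimum, the evaluations scheduled for EoS" and "AEs should be followed for at least 1 week after" the dose. Section 7.16 follows events that cause discontinuation until they resolve or stabilise. The treatment-emergent window runs "until 48 hours post-dose".
- **Nothing shows that the gaps fall on the least-tolerated treatment.** That is tempting to infer, but 4.4 lists seven reasons for withdrawal and Protocol 1.2 reports no adverse-event withdrawals in the programme so far. That section describes no co-administration with sumatriptan, so it does not settle the matter either way. The documents support only the narrower link through 7.6 and 7.7.
- **PK rules already exist.** Under SAP 6.4.9.1, when a sample is missing, "the pharmacokinetic analyses will be conducted as if that sample had not been scheduled for collection". A reader might conclude that a 4-hour AUC will bias the combination/alone ratio. But the same SAP section admits a profile only if its data describe it adequately, and Protocol 8.2.3 lists incomplete PK data and keeps the derived parameters out of the analysis. What remains is loose wording: the only example in 8.2.3 is a whole missing period, and SAP 6.2.3 needs one completed period and a subset of parameters.
- **The stakes are modest.** Vital signs and ECGs are summarised without a planned test, and the VAS and DEQ-5 are an exploratory endpoint. All orthostatic readings, 5 of 7 ECGs and 3 of 5 vital-sign times fall within 4 hours.

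None of this supplies a request for the later readings.

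**Conclusion.** The point holds as a gap in required data collection. For a subject who withdraws during a dosing period, the protocol stops asking for readings at 4 hours, although the dose has been taken and observation is planned to 30 hours. Withdrawals between periods, or at check-in for the next period, already have the full earlier profile and are not affected.

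The consequence is possible under-representation of strong responders in the 8-hour and 24-hour vital-sign and ECG summaries and in the VAS and DEQ-5 summaries. This rests on two assumptions: that some withdrawals occur within a period, and that some of them follow a marked early response. The documents make the second possible but give no frequency for either. The SAP's PD population (6.2.2) also requires a completed period without defining completion, so a subject who withdraws during Period 1 may leave that set altogether, whereas Protocol 8.2.3 keeps anyone dosed.

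The effect on PK power is small. The documents do not support a figure for bias in the geometric mean ratio, because that would need kinetics they do not give and would set aside the existing rules on incomplete profiles. This is a worthwhile, inexpensive improvement to the plan. It does not undermine the primary comparison.

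**What to change.** In Protocol 4.4, replace the 4-hour limit at the end of the sentence so that staff are asked to complete the assessments *scheduled for that dosing period (through 30 hours post-dose), where the subject agrees*. This concerns data collection only and leaves the decision to discontinue a subject unchanged.

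Secondarily, align SAP 6.2.3 and 6.4.9.1 with Protocol 8.2.3 by one sentence: an AUC(0-tlast) from a profile cut short by withdrawal is listed but not used in the combination/alone ratio.

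The cost is one sentence in each document. No procedure is added, and the unit stay is already planned to at least 30 hours. The drawback is that some subjects will decline to stay, so the gap will narrow but may not close.

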## 3.3.5 End-of-Study/Early Termination

The subjects are asked to return to the Phase 1 unit for the EoS assessments on Day 21 (+/- 2 days). The following procedures and assessments will be performed:

- Complete physical exam
- Serum pregnancy test (for all women)
- Safety 12-lead ECG
- Vital signs
- Safety clinical laboratory evaluations (hematology, chemistry and urinalysis)
- C-SSRS: Since the last visit.
- Adverse events
- Concomitant medications

• The subject's participation in the study is complete.

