## 7.11 Clinical Laboratory

### 7.11.1 Laboratory Parameters

Laboratory testing (hematology with differential, serum chemistry and urinalysis) will be performed using standard methods.

All subjects must fast at least 8 hours prior to any clinical laboratory assessment blood draw.

The urine screen for drugs of abuse will be performed at Screening and on Day -1 of each dosing period at check-in. Hepatitis B/C and HIV serology will be performed at Screening. Serum pregnancy testing will be done on all female subjects at Screening and EoS. Urine pregnancy testing will be completed on all female subjects on Day -1 of each dosing period at check-in. Clinical laboratory testing (CBC, chemistry, and urinalysis) will be performed at Screening, Day -1 of each dosing period, and EoS.

Table 3: List of Laboratory Tests

Hematology	Serum Chemistry	
RBC Hematocrit Hemoglobin Mean corpuscular hemoglobin (MCH) Mean corpuscular volume (MCV) Mean corpuscular hemoglobin concentration (MCHC) Platelet count WBC count (with differential) Neutrophils (granulocytes) Lymphocytes Monocytes Basophils Eosinophils	Creatinine Potassium (K+) Sodium (Na+) Chloride (CI-) Magnesium (Mg++) Glucose Urea Bilirubin (Total) Bilirubin (direct)	eGFR AST ALT AP Total Protein Albumin CO 2

**Urinalysis:** Macroscopic examination routinely including specific gravity, pH, protein, glucose, ketones, blood and urobilinogen. A microscopic examination will be performed if warranted based on macroscopic results.

**Urine drug screen:** A urine sample will be collected and analyzed (positive or negative) for drugs of abuse including amphetamine, opiate, cocaine, barbiturates benzodiazepines, and marijuana (tetrahydrocannabinol [THC]). For the Screening visit only, cotinine will be included in the urine drug screen panel.

**Serology:** Testing for HbsAg, Hepatitis C antibody and HIV 1 and 2 will be performed at the screening visit only. Results of each serology test will be reported as either positive or negative.

For females: A serum\_hCG test at the screening visit and EoS, urine\_hCG test on the day of Phase 1 unit admission for each of the three treatment periods (Day -1 of each dosing period).

AST: aspartate aminotransferase; ALT: alanine aminotransferase; AP: alkaline phosphatase; HbsAg: hepatitis B surface antigen; hCG: human chorionic gonadotropin; HIV: human immunodeficiency virus; RBC: red blood cell; WBC: white blood cell

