# 7.16 Follow-up of Adverse Events

All SAEs and any non-serious adverse events or laboratory abnormalities resulting in premature discontinuation will be followed until they have resolved, returned to baseline, or are determined to be chronic or stable by the Investigator or designee. Other non-serious adverse events should be followed through the EoS.

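### Section 4.4 tells only AE withdrawals to return for the EoS panel, in conflict with Section 3.3.5, so other dosed early leavers may have no closing AE inquiry or laboratory sample after the last dose

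*Protocol*

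**What the plan says.** **Who returns.** Protocol Section 4.4 has two tiers. For withdrawal after dosing for whatever reason, staff are to try to finish the assessments due up to 4 h post-dose. The next paragraph adds a closing visit when the subject is "withdrawn from the study due to an adverse event (clinical or laboratory), the subject will be instructed to return to the clinic", with the EoS evaluations as the minimum. Subject request, non-compliance, and Investigator or Sponsor request are listed as reasons for withdrawal but carry no return instruction.

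**The competing text.** Section 3.3.5 is headed for both End-of-Study and Early Termination. It lists the physical examination, ECG, vital signs, laboratory tests, C-SSRS and AEs, with no restriction by reason. Its only timing is Day 21 (±2).

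**When AE collection ends.** Sections 3.3.3.2 and 3.3.4 run it through EoS or early termination; Section 7.14.1 runs it to completion of EoS. Section 7.15 releases the Investigator from any duty to look actively for events in people who have left.

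**The windows.** Section 5.4.2 keeps subjects in the unit until at least 30 h post-dose. Section 7.14.2 counts TEAEs arising "after a subject ingested the dose of study drug until 48 hours post-dose". SAP Section 6.4.7 counts any onset or worsening from dosing onward, with no upper limit. Laboratory tests, under Section 7.11.1, "will be performed at Screening, Day -1 of each dosing period, and EoS".

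**Follow-up of known AEs.** Section 4.4 also says that "AEs should be followed for at least 1 week after the subject's dose of study medication". Section 7.16 says: "Other non-serious adverse events should be followed through the EoS."

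**The concern.** AEs are part of the primary endpoint in the synopsis, and Protocol Section 8.4.1 plans a model-based comparison of TEAE frequency between treatments. A subject's contribution should not depend on how a departure is labelled. Under the explicit rule in Section 4.4, two subjects who leave at the same hour after the same treatment can be observed differently. The one recorded as an AE withdrawal is recalled for an AE inquiry and laboratory tests; the one recorded as leaving on request is not. A label such as subject request may cover poor tolerability, so the loss could be informative. The by-treatment TEAE and laboratory summaries would then rest on ascertainment that varies with the recorded reason.

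Section 3.3.5 can be read as recalling everyone, so a site has two instructions and no early-termination timing to go with either.

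**Working it through.** The plan states no figure on this point, so there is none to reproduce. The check is timing arithmetic.

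**Inputs.** From the study-day table in Protocol Section 3.1: doses on study Days 1, 8 and 15; Day -1 of Periods 2 and 3 on study Days 7 and 14; EoS on Day 21 ± 2, i.e. Days 19 to 23. From Section 4.4: the 4 h minimum. From Section 5.4.2: discharge at 30 h or later. From Section 7.14.2: the 48 h TEAE window. From Section 8.1: at least 42 enrolled so that at least 36 complete.

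**1. Next scheduled contact for those who stay.**
- Dose 1 to the next Day -1: (7 − 1) × 24 = 144 h. Dose 2 to the next Day -1: (14 − 8) × 24 = 144 h.
- Dose 3 to EoS: (19 − 15) × 24 = 96 h to (23 − 15) × 24 = 192 h.

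All fall after 48 h, so anyone who attends the next visit has the window closed.

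**2. Window without required contact, under the literal Section 4.4 rule, for a non-AE leaver before the next visit.**
- Leaving at the 30 h discharge: 48 − 30 = 18 h; 18/48 = 37.5%.
- Leaving after the 4 h minimum: 48 − 4 = 44 h; 44/48 = 91.7%.

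These are shares of hours, not of expected events.

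**3. Section 3.3.5 applied as timed.** Day 21 ± 2 is 19 − 1 = 18 to 23 − 1 = 22 days after dose 1 for a subject who stops there, and 19 − 8 = 11 to 23 − 8 = 15 days after dose 2. The panel would take place, but long after the exposure it is meant to close.

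**4. Laboratory samples for a non-AE leaver who is not recalled.**
- Leaves after dose 1 and before study Day 7: no post-dose sample at all.
- Leaves after dose 2 and before study Day 14: has the Day 7 sample, none after dose 2.
- Leaves after dose 3: has the Day 7 and Day 14 samples, none after dose 3.

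**5. Who is not affected.** Section 7.12 terminates a subject with a positive breathalyzer at Day -1 of Period 2 or 3. That subject is at the unit about 144 h post-dose, where Section 3.3.2 schedules both AE and laboratory checks.

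**6. Upper bound on subjects.** 42 − 36 = 6, and 6/42 = 14.3%. Spread evenly over three treatments this is 2 subjects each, 2/42 = 4.8%. Reaching 14.3% for one treatment needs all six to be dosed, to leave for non-AE reasons, to leave before the next visit and to have had that treatment last.

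**7. The 1-week minimum.** EoS on Days 19, 20 and 21 is 4, 5 and 6 days after dose 3; Days 22 and 23 are 7 and 8 days after. On 3 of the 5 permitted days the visit falls short of one week.

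**The case against.** The strongest reply is that the panel for early leavers already exists. The heading of Section 3.3.5 covers early termination, its list is not limited by reason, and Sections 3.3.3.2 and 3.3.4 carry AE assessment through early termination. This stands to the extent that a reader might infer from Section 4.4 that the EoS panel is required only after an AE withdrawal, and the documents do not support that. They conflict. Section 3.3.5 does not settle the conflict, because it gives no early-termination timing and the overview schedule has no early-termination column.

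A reader might also infer that no non-AE leaver ever has the TEAE window closed, or that all of them lack post-dose laboratory data. Neither holds. Those terminated at a Day -1 check-in are seen in time, and a complete absence of post-dose samples is confined to subjects dosed only in Period 1 who leave before study Day 7.

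The 48 h limit is the protocol's alone. Under the SAP definition the percentages above do not apply. The absence of an upper limit lengthens the unobserved stretch; it does not remove it.

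It is tempting to add that the combination, or whichever treatment is least tolerated, would look better than it should. Nothing in the documents shows which treatment early leavers would have had last. Section 4.4 also requires the primary reason for every premature withdrawal to be determined and recorded, which partly guards against mislabelling.

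Finally, the 1-week sentence sits in the AE-withdrawal paragraph and concerns events already known. If it applies only there, it may not conflict with Section 7.16. It should be flagged, not counted as a second defect.

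**Conclusion.** The point holds as a conflict between Sections 4.4 and 3.3.5 with a practical consequence. A site that follows Section 4.4 to the letter may leave a dosed non-AE leaver without required contact for 18 to 44 of the 48 h protocol TEAE window, for departures between the 30 h discharge and the 4 h minimum. That subject also has no laboratory sample after the last dose.

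This rests on the subject leaving before the next scheduled visit and on Section 4.4 prevailing over the heading of Section 3.3.5. The six subjects come from the enrolment allowance; no dropout rate is stated. They are a ceiling under the planned numbers on missing inquiries, not a forecast and not a size of bias. The direction of any bias is not established. Sample size and power are unaffected. The change is still worth making, because it removes dependence on the recorded reason from a component of the primary endpoint at very little cost.

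**What to change.** - **Section 4.4:** apply the instruction to return for the Section 3.3.5 panel to every subject who leaves early after receiving study drug, whatever the reason.
- **Section 3.3.5:** time the early-termination panel from the subject's last dose instead of Day 21. Include an AE inquiry at or after the end of the TEAE window, by telephone if the visit is declined. For subjects who comply, the stretch of the 48 h window with no inquiry falls from 18 or 44 h to 0 h, and each who attends gains a laboratory sample after the last dose.
- **Reconcile:** Sections 3.3.3.2, 3.3.4, 3.3.5, 4.4 and 7.14.1 on who has the panel and when AE collection ends; Protocol Section 7.14.2 and SAP Section 6.4.7 on the TEAE window; and the 1-week minimum in Section 4.4 with Section 7.16 and an EoS visit 4 to 8 days after dose 3.

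The cost is protocol and SAP wording, plus one already-defined outpatient visit or a call for the few who leave early. The visit schedule for completers does not change. A subject may still decline both, so some loss can remain, but it would no longer be set by the recorded reason.
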